6.1.2 Exclusion Criteria

Patients will be excluded from the study if they meet any of the following criteria:

1. Hemoglobin < 10 g/dL prior to dosing on Day 1.
2. Transfusion dependency, defined as requiring 2 or more units of pack red blood cells per month for more than 3 months, or a hemoglobin level of ≤ 8 g/dL in the preceding 8 weeks before the start of dosing.
3. Eastern Cooperative Oncology Group (ECOG) questionnaire score of 3 or greater at Screening.
4. History of splenectomy.
5. Has undergone major surgery ≤ 4 weeks prior to starting study drug or has not recovered from side effects of such surgery.
6. Unresolved treatment related toxicities from prior therapies (unless resolved to \leq Grade 1).
7. Uncontrolled active infection.
8. Known positive for HIV if not well-controlled (i.e., undetectable viral load) or infectious hepatitis, type A, B or C.

Note for Italy: Active infection with hepatitis A virus, B virus (positive hepatitis B surface antigen; **note:** positive hepatitis B surface antibody and positive hepatitis B core antibody are not exclusionary provided disease is not active, which should be clearly documented in the patient's medical history) or C virus (patients with positive hepatitis C antibody result would require confirmation of active disease with a positive hepatitis C polymerase chain reaction (PCR) test), seropositivity for human immunodeficiency virus (HIV).

9. Current use of monoamine oxidase A and B inhibitors (MAOIs).

10. Evidence at the time of screening of increased risk of bleeding, including any of the following:
 - Activated partial thromboplastin time (aPTT) > 1.3 x the upper limit of normal
 - International normalized ratio (INR) >1.3 x the local upper limit of normal
 - History of severe thrombocytopenia or platelet dysfunction unrelated to a myeloproliferative disorder or its treatment
 - Known bleeding disorder (e.g., dysfibrinogenaemia, factor IX deficiency, hemophilia, Von Willebrand's disorder, Disseminated Intravascular Coagulation [DIC], fibrinogen deficiency, or other clotting factor deficiency).
11. Evidence at the time of Screening of significant renal or hepatic insufficiency (unless due to hemolysis, or leukemic infiltration) as defined by any of the following local lab parameters:
 - Calculated glomerular filtration rate (GFR; using the Cockcroft-Gault equation) <40 mL/min or serum creatinine > 1.5 x the local upper limit of normal
 - Aspartate transaminase (AST) or alanine aminotransferase (ALT) ≥ 2 x the local upper limit of normal
12. Current use of a prohibited medication (e.g., romiplostim) or expected to require any of these medications during treatment with the investigational drug.
13. Known immediate or delayed hypersensitivity reaction or idiosyncrasy to drugs chemically related to IMG-7289 or LSD1 inhibitors (i.e., monoamine oxidase inhibitors; MAOIs) that contraindicates their participation.
14. History of any illness/impairment of gastrointestinal (GI) function that might interfere with drug absorption (e.g., chronic diarrhea), confound the study results or pose an additional risk to the patient by participation in the study; patients with gastric bypass surgery.
15. Use of an investigational agent within less than 14 days, or the equivalent of at least 7 half-lives of that agent, whichever is the longer, prior to the study Day 1.
16. Females who are pregnant or breastfeeding or plan to become pregnant or breastfeed during the study.
17. A concurrent second active and non-stable malignancy (patients with a concurrent second active but stable malignancy, such as non-melanoma skin cancers, are eligible).

6.2 Patient Enrollment

A sufficient number of patients who fulfil the inclusion/exclusion criteria documented in Section 6.1 will be screened to ensure approximately 60 patients are enrolled and treated in this study.

6.3 Patient Withdrawal

In accordance with the Declaration of Helsinki, Good Clinical Practice (GCP), and International Council on Harmonization (ICH) Guidelines and applicable regulations governing human subject protection, a subject has the right to withdraw from the study at any time for any reason. Subjects may also be removed from the study by the Sponsor or Investigator. CCI

[REDACTED] Patients will be requested to return for follow-up beginning with an End of Treatment visit as per Section 9.6.1.

The Sponsor or Investigator may remove patients from the study for various reasons, including:

- Taking another investigational medicinal agent during their involvement in the study;
- Use of a prohibited medication;
- Major violation of, or deviation from, study protocol procedures which, in the judgment of the Medical Monitor, could adversely affect the patient or the integrity of the study including missing an extended duration of IMG-7289 doses or other evidence of major non-compliance;
- Withdrawal from the study is, in the Investigator's judgment, in the patient's best interest;
- Experiencing a Dose Limiting Toxicity (DLT), as per Section 8.2.2.

CCI

6.5 Guidelines

Patient safety is paramount. The guidelines provided below are intended to provide some consistency across sites by providing guidance to be used by the Investigator, the study staff and the patient to safeguard patient safety while maintaining data integrity. The guidelines are not intended to supersede best clinical judgment by the Investigator. Please contact the Medical Monitor with questions or with planned/known divergences from these guidelines.

1. In general, supportive care (transfusions, administration of anti-fungals, etc.) should be maintained in accordance with institutional policy.
2. Patients taking medications with the potential to induce or inhibit CYP_{3A4} or CYP_{2D6} should be monitored closely for potential effects of co-administration; particular attention should be given to anti-infectives in the azole class.
3. Cessation of IMG-7289 is invariably associated with a rebound in thrombopoiesis and platelet counts may easily exceed the baseline value. When IMG-7289 is discontinued, the platelet count should be monitored closely and an alternative cytreductive therapy to lower platelets should commence within 24-48 hours.

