12. Current use of a prohibited medication (e.g., romiplostim) or expected to require any of these medications during treatment with the investigational drug.
13. Known immediate or delayed hypersensitivity reaction or idiosyncrasy to drugs chemically related to IMG-7289 or LSD1 inhibitors (i.e., monoamine oxidase inhibitors; MAOIs) that contraindicates their participation.
14. History of any illness/impairment of gastrointestinal (GI) function that might interfere with drug absorption (e.g., chronic diarrhea), confound the study results or pose an additional risk to the patient by participation in the study; patients with gastric bypass surgery.

15. Use of an investigational agent within less than 14 days, or the equivalent of at least 7 half-lives of that agent, whichever is the longer, prior to the study Day 1.
16. Females who are pregnant or breastfeeding or plan to become pregnant or breastfeed during the study.
17. A concurrent second active and non-stable malignancy (patients with a concurrent second active but stable malignancy, such as non-melanoma skin cancers, are eligible).

GUIDELINES: These guidelines are for use by the Investigator, study staff and patient to safeguard patient safety while maintaining data integrity.

1. In general, supportive care (transfusions, administration of anti-fungals, etc.) should be maintained in accordance with institutional policy.
2. Patients taking medications with the potential to induce or inhibit CYP_{3A4} or CYP_{2D6} should be monitored closely for potential effects of co-administration; particular attention should be given to anti-infectives in the azole class.
3. Cessation of IMG-7289 is invariably associated with a rebound in thrombopoiesis and platelet counts may easily exceed the baseline value. When IMG-7289 is discontinued, the platelet count should be monitored closely and an alternative cyto-reductive therapy to lower platelets should commence within 24-48 hours.

CCI

Management of Study Toxicities: Adverse event intensity will be evaluated using the National Cancer Institute (NCI) Common Terminology Criteria for Adverse Events (CTCAE) version 5, published 27 November 2017. Please refer to Section 8.2 for additional detail on management of study toxicities, including reduction of the starting dose based on dose limiting toxicity (DLT).

Definitions:

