Hematologic Toxicity: Hematologic values outside of the normal reference range are inherent features of MPNs and are expected effects of many therapeutic attempts to manage these diseases. The effects of IMG-7289 on normal myeloid hematopoiesis observed in non-clinical and clinical studies are expected; these are pharmacodynamic effects of LSD1 inhibition by IMG-7289, thus are not regarded as adverse. These events, with the exceptions below, will not be considered DLTs.

Dose limiting toxicity (DLT): Any one of the following AEs that occurs through Day 7 of the Initial Treatment Period and is considered by the Investigator to be possibly, probably or definitely related to IMG-7289:

- Any Grade 2 or above thrombocytopenia associated with clinically significant bleeding*
- Any Grade 3 or above thrombocytopenia;
- Any Grade 4 or 5 non-hematologic adverse event;
- Any Grade 3 or above non-hematologic adverse event with failure to recover to Grade 2 within 7 days of drug cessation, with the following exceptions:
 - nausea, vomiting or diarrhea that responds to standard medical care
 - aesthenia lasting less than 14 days
- Any Grade 3 electrolyte abnormality unrelated to the underlying malignancy (for example, hyperkalemia *is* related to thrombocytosis and would therefore not qualify as DLT) and persisting greater than 24 hours.

*Clinically significant bleeding is defined as an event that is life-threatening, cannot be controlled and/or results in hemodynamic instability.

Patients who experience a DLT may have their dose adjusted downward if the Medical Monitor and Principal Investigator (PI) deem it safe for the patient to continue on IMG-7289. Any patient that experiences DLT that results in discontinuation of IMG-7289 therapy may begin alternative cytoreductive therapy to lower platelets within 24-48 hours.

Please contact the Imago medical monitor to discuss IMG-7289 dose modifications for the management of clinically significant changes in platelets, neutrophil counts, or other hematologic parameters.

Stopping Rules:

IMG-7289 will be discontinued in the event of the following:

- Post DLT, the Medical Monitor and Principal Investigator deem it unsafe for the patient to continue on IMG-7289.
- Post dose reduction due to DLT, the patient fails to demonstrate significant improvement within 21 days.

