- Post temporary interruption of IMG-7289 due to platelet counts below 50 k/ μ L ($50 \times 10^9/L$), the patient's platelet counts don't return to >150 k/ μ L ($150 \times 10^9/L$) within 21 days.

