6.6 Prohibited Medications

Please consult the Medical Monitor with any questions pertaining to prohibited medications.

1. All cytotoxic agents, including standard-of-care therapies for ET
2. All hematopoietic growth factors: romiplostim, eltrombopag, granulocyte and granulocyte-macrophage colony stimulating factor (G-CSF and GM-CSF) and erythropoietin (EPO)
3. Monoamine oxidase A and B inhibitors
4. Anticoagulant and nonsteroidal anti-inflammatory drug (NSAID; including aspirin) use are only prohibited in patients when their platelet count is < 50 k/ μ L (50×10^9 /L)

CCI

CCI [REDACTED]

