8.2.2 Dose Limiting Toxicity (DLT)

DLT is defined as any one of the following AEs that occurs through Day 8 of the ITP and is considered by the Investigator to be possibly, probably or definitely related to IMG-7289:

- Any Grade 2 or above thrombocytopenia associated with clinically significant bleeding*
- Any Grade 3 or above thrombocytopenia;
- Any Grade 4 or 5 non-hematologic adverse event;
- Any Grade 3 or above non-hematologic adverse event with failure to recover to Grade 2 within 7 days of drug cessation, with the following exceptions:
 - nausea, vomiting or diarrhea that responds to standard medical care
 - aesthenia lasting less than 14 days
- Any Grade 3 electrolyte abnormality unrelated to the underlying malignancy (for example, hyperkalemia *is* related to thrombocytosis and would therefore not qualify as DLT) and persisting greater than 24 hours.

*Clinically significant bleeding is defined as an event that is life-threatening, cannot be controlled and/or results in hemodynamic instability.

Patients who experience DLT will have their dose adjusted downward if the Medical Monitor and Principal Investigator deem it safe for the patient to continue on IMG-7289. Any patient that experiences DLT that results in discontinuation of IMG-7289 therapy may begin alternative therapy within 24-48 hours of discontinuation if their physician deems this safe and appropriate regarding the resolution of the DLT.

Please consult the Medical Monitor for IMG-7289 dose modifications for the management of clinically significant changes in platelets, neutrophil counts, or other hematologic parameters.

CCI

Term	Protocol Meaning
Collect MPN-SAF	MPN-SAF is to be completed by the patient in their native language and in the format provided. The MPN-SAF will be completed during Screening (as close to Day -7 as possible), pre-Dose Day 1 and weekly from Day 7 through the EoS Visit. Ideally, the MPN-SAF will be completed at the same time and day each week for consistency. On visit days, the MPN-SAF should be completed prior to the study visit, and if the patient arrives without a completed MPN-SAF, then it will be completed during the visit and collected prior to the patient departing. Importantly, multiple MPN-SAF forms will need to be provided to the patient for completion between visits, during each 'off week'. Date of completion should be documented on each MPN-SAF completed.

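### For a DLT that ends treatment, the protocol gives three different instructions on alternative therapy and two on dose adjustment, and the general instruction makes no visible exception for patients stopped for low platelets

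*Protocol*

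**What the plan says.** **Therapy after stopping, any reason.** Item 3 of the synopsis guidelines says that "an alternative cyto-reductive therapy to lower platelets should commence within 24-48 hours". Section 6.5, item 3, has the same instruction ("should commence within 24-48 hours"), as does Section 3.5, item 3. All three give the same reason: platelets rebound after the drug is stopped and can exceed baseline.

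**Therapy after a DLT that ends treatment.** The synopsis DLT text says that the patient "may begin alternative cytoreductive therapy to lower platelets within 24-48 hours" and attaches no condition. Section 8.2.2 says that the patient "may begin alternative therapy within 24-48 hours of discontinuation if their physician deems this safe and appropriate regarding the resolution of the DLT".

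**Dose after a DLT, if treatment continues.** The synopsis reads "Patients who experience a DLT may have their dose adjusted downward". Section 8.2.2 reads "Patients who experience DLT will have their dose adjusted downward". Both apply only if the Medical Monitor and the Principal Investigator consider it safe to go on.

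**Stopping for low platelets.** Two of the DLT criteria, in the synopsis and in Section 8.2.2, are thrombocytopenia: Grade 3 or above, or Grade 2 or above with clinically significant bleeding. A synopsis stopping rule ("Post temporary interruption of IMG-7289 due to platelet counts below 50" k/µL) ends treatment when the count has not come back above 150 k/µL within 21 days.

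**The concern.** A site that has to act on a DLT will find a different instruction depending on the page it opens. The synopsis disagrees even with itself, since its guideline and its DLT paragraph use different verbs for the same event.

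The low-platelet stops make this more than a question of style. Taken literally, the general instruction tells sites to start treatment that lowers platelets in a patient who was stopped because platelets were already too low. Section 3.5, item 1, names severe thrombocytopenia as the largest clinical risk of the drug, and safety and tolerability is a primary objective (Section 4.2.1). Inconsistent handling of these patients would bear on their safety first. It would also affect how comparable the safety data are between sites.

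**Working it through.** No figure in the plan has to be reproduced. The check is which sentences apply to the same patient, and whether they agree.

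| Patient | General guideline (synopsis, 3.5, 6.5) | Synopsis DLT text | Section 8.2.2 |
|---|---|---|---|
| A. Stopped for a non-hematologic DLT | should start | may start, no condition | may start, if judged safe and appropriate |
| B. Stopped for a thrombocytopenia DLT | should start | may start, no condition | may start, if judged safe and appropriate |
| C. Stopped under the platelet non-recovery rule | should start | not applicable | not applicable |
| D. DLT, treatment continues | not applicable | dose *may* be reduced | dose *will* be reduced |

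**Rows A and B.** The general guideline covers every discontinuation, so it overlaps fully with the two DLT texts. Three strengths of instruction therefore govern one event: a recommendation, an open permission, and a permission tied to the physician's judgment about resolution of the DLT. The object differs too. The guideline and the synopsis speak of therapy to lower platelets, whereas Section 8.2.2 speaks only of alternative therapy.

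**Row B.** Here the mismatch matters most. The reason for stopping is a low count, and the general guideline still calls for platelet-lowering therapy. Only Section 8.2.2 makes the start depend on how the DLT is resolving.

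**Row C.** By the terms of the rule, the count fell below 50 k/µL and did not return above 150 k/µL within 21 days. That patient is already well under the 400 k/µL target of the primary efficacy endpoint. Only the general guideline speaks to this patient in the visible text, and it has no exception. There is no three-way conflict here; the gap is the missing statement.

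**Row D.** The safety condition is the same in both places, so it cannot explain the change from *may* to *will*. Under the synopsis wording a patient may continue at an unchanged dose; under Section 8.2.2 that is not an option.

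**How long rows A, B and D can arise.** A DLT counts only through Day 7 in the synopsis and through Day 8 in Section 8.2.2. Those two windows also need to be made the same.

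**The case against.** The strongest reply is that the protocol already leaves this to the physician. Section 6.5 states that its guidelines do not override the investigator's best clinical judgment, and it asks sites to raise planned departures with the Medical Monitor. Read that way, *should* in Section 6.5 comes close to the conditional permission in Section 8.2.2. The expected rebound may also be why the sponsor wants early therapy even where counts are low. In addition, the synopsis sends readers to Section 8.2 for more detail on managing toxicity.

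This softens the conflict without removing it. The deference to judgment is not repeated in the synopsis or in Section 3.5. A reference to further detail does not say which text prevails when they differ. The rebound rationale is given for cessation in general and does not say how it applies when the count is already low. None of this accounts for *may* against *will*.

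Redaction limits the point. Section 8.2.3 and the titration table are not in the public text, so the absence of an exception can be asserted only for what is visible. The conflicting sentences themselves are all visible.

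A reader might also infer more than the documents support:

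- **That every patient who stops is affected, about 60 in all.** For stops other than a DLT, the visible text consistently says *should*.
- **That the list in Section 6.6 ("All cytotoxic agents, including standard-of-care therapies for ET") forbids the alternative therapy during follow-up.** Exclusion criterion 12 ties prohibited medication to the period of treatment with the study drug, Section 6.5 expressly expects alternative therapy after stopping, and text after Section 6.6 is redacted.
- **That a patient continued without a dose reduction escapes the stopping rules.** The 21-day rule after dose reduction would not reach that patient, but the first stopping rule covers anyone judged unsafe to continue after a DLT, and Section 6.3 lists a DLT as a reason for removal.
- **That the primary efficacy test is compromised.** That test is at Day 169 (SAP 6.3.1), and the wording conflict does not bear on it directly.

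**Conclusion.** The inconsistency is in the current text and should be corrected. There are three instructions on alternative therapy for a DLT that ends treatment, and two on dose adjustment for a DLT that does not. Separately, the general instruction has no visible exception for patients stopped because platelets are low.

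The reach is narrow. The three-way conflict applies only to discontinuations for a DLT arising in roughly the first week. The low-platelet overlap applies to thrombocytopenia DLTs and to stops under the non-recovery rule, which is not limited to that week. The documents give no rate for either, so no count is offered. The importance comes from the kind of patient concerned, not from the number.

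The conclusion assumes that the redacted sections contain no sentence ranking these texts or making the exception. It takes no position on which instruction is clinically right.

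**What to change.** At the next amendment, reconcile the synopsis (guidelines, DLT text and stopping rules) with Sections 3.5, 6.5 and 8.2.2, and with Section 8.2.3 if it differs, so that:

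- one statement governs alternative therapy after discontinuation and says expressly how it applies to patients stopped for low platelets;
- one wording governs dose adjustment after a DLT;
- the DLT window is the same in the synopsis and Section 8.2.2.

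The sponsor's medical team decides the content. The cost is protocol wording only.

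Optionally, the SAP could flag adverse events and platelet counts recorded after alternative therapy starts, because treatment-emergent events run through the end of the study (SAP 6.4.1) and laboratory summaries run to the end-of-study visit (SAP 6.4.4). This is a refinement: SAP 6.2.5 already codes and tabulates concomitant medications under a definition that would include such therapy.

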6.6 Prohibited Medications

Please consult the Medical Monitor with any questions pertaining to prohibited medications.

1. All cytotoxic agents, including standard-of-care therapies for ET
2. All hematopoietic growth factors: romiplostim, eltrombopag, granulocyte and granulocyte-macrophage colony stimulating factor (G-CSF and GM-CSF) and erythropoietin (EPO)
3. Monoamine oxidase A and B inhibitors
4. Anticoagulant and nonsteroidal anti-inflammatory drug (NSAID; including aspirin) use are only prohibited in patients when their platelet count is < 50 k/ μ L (50×10^9 /L)

CCI

CCI [REDACTED]

7.2 Dispensing, Administration, Dosage and Missed Doses

7.2.1 Dispensing

All material supplied is for use only in this clinical study and should not be used for any other purpose. Only patients enrolled in the study may receive study drug, in accordance with all applicable regulatory requirements. Only authorized site staff may dispense study drug.

The Investigator is responsible for IMG-7289 accountability, reconciliation and record maintenance (Section 14.5). CCI [REDACTED]

[REDACTED]

